### **Number of subjects**

- 30 stratified to recruit 10-15 subjects with a baseline PIF < 60 l/min at with an Incheck level 2 resistance

### **Ellipta Device Selection**

- the Ellipta is the most commonly used DPI device in the United States
- the medium/low (level 2) resistance setting on the InCheck Dial device closely approximates the resistance found in the Ellipta device
- suggested peak inspiratory flows of 60 l/min for suboptimal and 30 l/min for minimal are most commonly based on using the medium/low (level 2) resistance setting on the InCheck Dial device
- manufacturer recommendations for Ellipta device usage describe the inspiratory effort required as a “breathe out fully, then take one long, steady, deep breath”.

### **Trelegy Selection**

- Trelegy is an effective COPD therapy shown to produce maximal bronchodilation in patients with COPD, both acutely (day 1) and chronically
- A low PIF likely has the greatest incidence in more severe COPD patients who require triple therapy
- Use of Trelegy as compared to a LABA/LAMA eliminates any concern over ICS withdrawal in patients with chronic ICS usage prior to study participation and ads minimal risk to those not taking an ICS prior to study participation
- All subjects will have their maintenance COPD medications discontinued and will be provided Trelegy Ellipta maintenance therapy throughout the study

### **Visit 1**

#### **Consent**

#### **Baseline Measurements**

- Demographics
- History and Physical
- CAT
- Exacerbation history in the last year (# moderate and # severe)
- Pre Ventolin PIF measured with the Incheck Valve set to a low/mid level 2 resistance and measured after instructions to exhale fully followed by a sharp maximal inhalation (minimum of 3 efforts)
- Pre and 15-30 minutes Post Ventolin spirometry

### **Visit 2 (1-8 days post visit 1)**

#### **Pre Dose Measurements**

- Review COPD medications and ensure effective washout
  - prn SAMA/SABA at least 6 hours
  - bid LAMA, LAMA/LABA or LABA/ICS at least 12 hours
  - qd LAMA, LAMA/LABA, LABA/ICS or LAMA/LABA/ICS at least 24 hours
- Adverse Event assessment

- PIFR measured with the In-check Dial resistance set at R2, low/mid (e.g. Ellipta)
  - Technique 1  
Standing, “exhaling fully” (after instructions, but without coaching to full exhalation), “deep full inhalation”
  - Technique 2  
Sitting, “exhaling fully” (after instructions, but without coaching to full exhalation), “deep full inhalation”
  - Technique 3  
Sitting, “exhaling fully” (after instructions, but without coaching to full exhalation), “sharp maximum inhalation”
  - Technique 4  
Sitting, “exhaling fully to RV” (with coaching to exhale completely before effort), “sharp maximum inhalation”
    - Minimum of 3 efforts performed at each setting, best effort recorded
- Inspiratory Capacity
- Spirometry with flow volume loops and inspiratory flows

**Intervention 1** – Trelegly Ellipta 1 puff

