What level of reproducible effort is needed to provide a reliable PIF measurement is also uncertain. Three efforts has been suggested, but the variability allowed between efforts and whether the best or average PIFR should be used is also unclear. These decisions become critically important when performing “effort-dependent” testing, since variable submaximal efforts will give inadequate results and could inappropriately define a patient with a “suboptimal” PIF when, in fact, they are fully capable of inhaling sufficiently to use a DPI.

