### **Secondary**

- Determine if a suboptimal or a minimal PIF in COPD patients predicts clinical response to medication delivered using the Ellipta DPI device.
- Determine the best way to measure PIF for the Ellipta device and are there suboptimal or minimal PIF thresholds that can be identified to predict response to a DPI?
  - What inspiratory effort should a patient exert when measuring PIF?
  - What lung volume should a patient start from when measuring PIF?
  - What reproducibility criteria should be used when measuring PIF?
- Determine if best PIF correlates with FEV1, FVC, IC or peak inspiratory flow measured during spirometry.

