##### **Secondary**

- Acceptability and Reproducibility of PIF Testing during various testing efforts
- Correlation of various methods of PIF Testing to
  - Acute (visit 2) IC and FEV1 response to Trelegy Ellipta
  - Added benefit of Ventolin to Trelegy Ellipta
  - Chronic (visit 3) IC and FEV1 response to Trelegy Ellipta
- Predictors of Trelegy Ellipta response

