### **Statistical Plan of Analysis**

A change in FEV1 of less than 50 ml has been defined by many studies as a level of bronchodilation that defines non-inferiority between bronchodilators. However, a comparative study between Anoro and Spiriva determined that to achieve a 1 sided 2.5% significance level with a within subject standard deviation of 140 ml and a 90% power to detect 50 ml noninferiority would require a sample size of 220 patients to determine non-inferiority. Although within subject standard deviation for short-acting bronchodilator after long acting bronchodilator in COPD patients with an FEV1 <50% predicted likely has a smaller FEV1 standard deviation, the projected numbers to determine non-inferiority in this study are too large to be obtained by a single center.

We therefore propose this study as an observational and an exploratory study that will likely be underpowered for meaningful comparison. Noninferiority and subsequent superiority will be assessed within the study to provide estimates for potential future evaluations. Our proposed numbers are in line with previously reported studies that have been used for current recommendations for suboptimal and minimal PIF measures. In spite of these statistical limitations, we believe this information will provide significant added information about PIF and the use of the Ellipta device.

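### Recording only the best PIF effort per technique at Visits 2 and 3 leaves no data for the between-effort reproducibility and acceptability endpoint

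*Combined protocol and SAP*

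**What the plan says.** Under Pre Dose Measurements, Visits 2 and 3 each list four PIF techniques and close with the same rule: "Minimum of 3 efforts performed at each setting, best effort recorded". No other section asks for the remaining efforts, the number of attempts or an acceptability judgement on each effort.

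Visit 1 (Baseline Measurements) has one manoeuvre, full exhalation "followed by a sharp maximal inhalation (minimum of 3 efforts"), and does not say which value or values are kept.

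Three places set the aim that these data must serve:

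- Study Endpoints, Secondary, first item: "Acceptability and Reproducibility of PIF Testing during various testing efforts".
- Objectives/Questions, Secondary, as a sub-question: "What reproducibility criteria should be used when measuring PIF".
- PIF Measurement Technique, which gives the reason for asking: "the variability allowed between efforts and whether the best or average PIFR should be used is also unclear". The section goes on to describe these decisions as critical for an effort-dependent test, because variable submaximal efforts could wrongly label a patient as having a suboptimal PIF.

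**The concern.** A reproducibility criterion for an effort-dependent test states how closely a patient's repeated efforts must agree before the result is accepted. Setting one requires the individual efforts. A rule that keeps only the maximum discards the information this endpoint is about.

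If sites follow the text exactly, the study cannot say how much between-effort variation to allow, which technique gives the most consistent efforts, or what fraction of efforts is acceptable. It also cannot compare the best with the average value, which the background raises as an open question. Efforts not written down at the visit may not be recoverable later.

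**Working it through.** The documents give no figure for PIF reproducibility, so there is none to reproduce. The check is whether the recorded data identify the quantity wanted.

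**Inputs.** 30 patients (Number of subjects); 4 techniques, 2 visits and at least 3 efforts (Visits 2 and 3, Pre Dose Measurements). I assume all 30 complete both visits and make exactly 3 efforts per technique.

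**1. Values kept and lost**

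- Performed: 30 × 4 × 2 × 3 = 720 (24 per patient).
- Recorded: 30 × 4 × 2 = 240 (8 per patient).
- Not recorded: 720 − 240 = 480, or two thirds. More than 3 efforts per technique would raise this.

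**2. Degrees of freedom for between-effort variability**

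- As written: one value per session, so 1 − 1 = 0 per patient and 0 overall.
- With every effort captured: 30 × (3 − 1) = 60 per technique per visit, or 60 × 4 × 2 = 480 in all.

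**3. The maximum does not determine the spread.** Illustration with assumed values:

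| Efforts (L/min) | Recorded | Mean | SD | CV | Best minus second |
|---|---|---|---|---|---|
| 62, 61, 60 | 62 | 61 | 1.0 | 1.6% | 1 |
| 62, 50, 38 | 62 | 50 | 12.0 | 24% | 12 |

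Both patients enter the database as 62. The second is above the 60 L/min threshold on the best effort and below it on the mean.

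**4. Between-visit data cannot stand in.** Let sw be the between-effort SD, sb the between-visit SD, and D the SD of the Visit 2 to Visit 3 differences in best value. For exactly 3 independent normal efforts, the variance of the best is 0.559 sw², so

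D² = 2(sb² + 0.559 sw²).

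This is one equation in two unknowns:

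- sw = 0 gives sb = D/√2 = 0.71 D.
- sb = 0 gives sw = D/√1.118 = 0.95 D.

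Under these assumptions the observed D is compatible with any between-effort SD from 0 to 0.95 D.

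**5. Precision if every effort were captured.** With 60 degrees of freedom, the 95% confidence factors for the within-session SD are √(60/χ²₀.₉₇₅) = 0.849 and √(60/χ²₀.₀₂₅) = 1.217, or about −15% to +22%. For the percentage of patients meeting a candidate repeatability limit, an illustrative 24 of 30 (80%) has a Wilson 95% CI of 63% to 90%.

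**The case against.** **The rule may mean something milder.** The text does not say that only the best effort is recorded. In a short protocol without a CRF or data-management section, the phrase may mean that the best effort is the value taken for analysis. That is possible, and it would be odd to pose the between-effort question and then discard the efforts on purpose. But this is the only recording instruction, nothing elsewhere provides for keeping the rest, and site staff would naturally write down the best. Even on the milder reading the text needs a sentence.

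**The endpoint may be about techniques.** The various efforts it mentions could be the four techniques, and acceptability could mean whether a patient can perform a technique at all. Reproducibility of the best value between Visits 2 and 3 would then partly meet it. This stands as far as it goes: that comparison can be made for all four techniques. However, Visit 2 follows washout and Visit 3 follows about two weeks of study treatment, so it mixes measurement error with treatment effect. It also leaves unanswered the between-effort question that the background poses.

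**Visit 1 has no best-effort rule.** True, so within-session data for its one manoeuvre are not ruled out. They are not required either, and one manoeuvre cannot supply data for four techniques.

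**The 0.95 D limit is not general.** Correct. It needs exactly 3 independent normal efforts; with 5 the variance of the best is about 0.448 sw² and the limit about 1.06 D. Learning or fatigue would break independence. The lack of identifiability does not depend on the exact limit.

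**The study is declared exploratory and probably underpowered.** That limits the consequences, but the Statistical Plan of Analysis justifies the study as a source of estimates for future work, and effort-level variability is one such estimate.

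**Conclusion.** The concern holds. Followed literally, the recording rule at Visits 2 and 3 leaves 0 within-session degrees of freedom for a listed secondary endpoint and for the sub-question on reproducibility criteria; at least 480 of 720 efforts go unrecorded. The counts assume 30 completers and three efforts per technique. The conclusion rests on reading the rule as the complete capture instruction, which is the natural reading because no other is given.

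The damage is bounded. The primary endpoints, the sub-questions on inspiratory effort and starting lung volume, and between-visit repeatability of the best value can all still be addressed. This should be fixed before data collection, but it does not threaten the study's main comparison.

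**What to change.** - At Visits 1, 2 and 3, record the value, order and acceptability of every PIF effort. Keep the best as the analysis value.
- State what makes a PIF effort acceptable; the documents do not define this.
- By technique, report the within-session SD, CV and ICC, and the percentage of patients meeting candidate repeatability limits.
- Report between-visit repeatability of the best value separately, noting the intervening treatment.
- Best versus mean can be added as an exploratory analysis.

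If the rule was meant only to name the analysis value, one sentence stating that all efforts and their acceptability are captured resolves the capture problem.

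The cost is a few CRF fields: at least 3 values and 3 flags per technique per visit in place of 1 value. The efforts are already being performed, so no manoeuvres, visits or patients are added.

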**Post Trelegly Ellipta Measurements**

- IC – 115 minutes post dosing with Trelegly Ellipta
- Spirometry – 30, 60, 120 minutes post dosing with Trelegly Ellipta

**Intervention 2** – Ventolin pMDI 2 puffs with spacer

(to be given after 120 minutes post Trelegly Ellipta spirometry is completed)

**Post Ventolin pMDI Measurements**

- IC – 55 minutes post dosing with Ventolin
- Spirometry – 30 and 60 minutes post dosing with Ventolin

**Intervention 3** – Trelegly Ellipta QD x 2 weeks

**Visit 3** (12-14 days post visit 2)

**Pre Dose Measurements**

- Review COPD medications and ensure adherence to Trelegly therapy
- Adverse Event assessment
- PIFR measured with the In-check Dial resistance set at R2, low/mid (e.g. Ellipta)
  - Technique 1  
Standing, “exhaling fully” (after instructions, but without coaching to full exhalation), “deep full inhalation”
  - Technique 2  
Sitting, “exhaling fully” (after instructions, but without coaching to full exhalation), “deep full inhalation”
  - Technique 3

Sitting, “exhaling fully” (after instructions, but without coaching to full exhalation), “sharp maximum inhalation”

- Technique 4  
Sitting, “exhaling fully to RV” (with coaching to exhale completely before effort), “sharp maximum inhalation”
- Minimum of 3 efforts performed at each setting, best effort recorded
- Inspiratory Capacity
- Spirometry with flow volume loops and inspiratory flows

#### **Intervention 1 – Trelegy Ellipta 1 puff**

##### **Post Trelegy Ellipta Measurements**

- IC – 115 minutes post dosing with Trelegy Ellipta
- Spirometry – 30, 60, 120 minutes post dosing with Trelegy Ellipta

#### **Intervention 2 – Ventolin pMDI 2 puffs with spacer**

(to be given after 120 minutes post Trelegy Ellipta spirometry is completed)

##### **Post Ventolin pMDI Measurement**

- IC – 55 minutes post dosing with Ventolin
- Spirometry – 30 and 60 minutes post dosing with Ventolin

#### **Study Endpoints**

##### **Primary**

- Post BD response to Trelegy Ellipta at Visits 2 and 3 by PIF (normal, suboptimal, minimal)
- Post BD added response to Albuterol after Trelegy Ellipta at Visits 2 and 3 by PIF (normal, suboptimal, minimal)

##### **Secondary**

- Acceptability and Reproducibility of PIF Testing during various testing efforts
- Correlation of various methods of PIF Testing to
  - Acute (visit 2) IC and FEV1 response to Trelegy Ellipta
  - Added benefit of Ventolin to Trelegy Ellipta
  - Chronic (visit 3) IC and FEV1 response to Trelegy Ellipta
- Predictors of Trelegy Ellipta response

#### **Safety Data Collection**

- Any adverse event determined by the principal investigator/designee to a) put the subject at clinical risk or b) to make the subject unable to perform appropriate clinical testing during a visit
  - in the event that such an event occurs, a visit may be re-scheduled for up to 1 week later

- Any serious adverse event considered to be reasonably attributed to Trelegy Ellipta study medication/medical device by the principal investigator/designee, regardless of the investigator/external parties expectedness assessments.
- Any medical device (Ellipta) incidents or malfunction
- Pregnancy in any subject exposed to Trelegy Ellipta study medication/medical device
- All events will be reported in a non-statistical tabular format

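### The only rule for serious adverse events covers events attributed to Trelegy Ellipta, so the event table cannot guarantee a complete all-cause SAE count

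*Combined protocol and SAP*

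**What the plan says.** Safety Data Collection is the only section that sets out which safety events are collected. It has two items on adverse events:

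- The first takes "Any adverse event determined by the principal investigator/designee to a) put the subject at clinical risk", or to leave the subject unable to do the visit's testing. It has no causality or product condition.
- The second, on serious events, takes "Any serious adverse event considered to be reasonably attributed to Trelegy Ellipta study medication/medical device by the principal investigator/designee". It ends with "regardless of the investigator/external parties expectedness assessments", so expectedness is waived and attribution is not.

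The section also collects "Any medical device (Ellipta) incidents or malfunction" and pregnancies after exposure to Trelegy Ellipta. It closes with "All events will be reported in a non-statistical tabular format".

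Other sections impose interventions besides Trelegy:

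- Visit 1 includes spirometry before and after Ventolin. Visits 2 and 3 each include "Ventolin pMDI 2 puffs with spacer".
- Trelegy Selection states that "All subjects will have their maintenance COPD medications discontinued", with Trelegy Ellipta supplied in their place.
- The pre-dose list for Visit 2 requires staff to "Review COPD medications and ensure effective washout", with intervals of at least 6, 12 or 24 hours by drug class.
- Visits 2 and 3 each require four PIF techniques, plus repeated inspiratory capacity and spirometry.

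**The concern.** The SAE item makes causality a condition of collection, for one product. The usual order is to collect every serious event and then record what the investigator thinks caused it. Here the causality judgement comes first, and an event that fails it need not be recorded as serious at all.

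The patients have a post-bronchodilator FEV1 below 50% predicted (Study Population), and the protocol asks more of them than taking Trelegy. A cardiac event after Ventolin, or an admission during washout, would not naturally be attributed to Trelegy. What is at stake is whether the investigators can state, at the end, how many serious adverse events of any cause occurred. No efficacy endpoint depends on it.

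**Working it through.** No power, margin or sample-size calculation bears on this point. The check is to compare the sections and then size the consequence.

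**1. Is there a wider SAE rule elsewhere?** No. The pre-dose lists for Visits 2 and 3 each include an adverse event assessment, without definitions or rules. A safety follow-up contact is mentioned only in the contraception criterion under Study Population, without content or timing.

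**2. What the protocol imposes, set against the two items.**

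| Source of risk | When | SAE item | First item |
|---|---|---|---|
| Ventolin test | Visit 1, before study Trelegy | Cannot be met | If judged a clinical risk or unable to test |
| Washout | Before the Visit 2 dose | Cannot be met | Same |
| PIF, capacity and spirometry efforts before dosing | Visit 2 | Cannot be met | Same |
| Ventolin | Visits 2 and 3, after Trelegy | Only if attributed to Trelegy Ellipta | Same |
| Replacement of maintenance drugs by Trelegy | From Visit 2 | Only if attributed to Trelegy Ellipta | Same |
| Later effort-dependent tests | Visits 2 and 3 | Only if attributed to Trelegy Ellipta | Same |

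The first three rows follow from timing. The visit schedule first gives study Trelegy as Intervention 1 at Visit 2, and an event cannot be attributed to a study drug not yet given. Trelegy Selection speaks of Trelegy being provided throughout the study; the table follows the visit schedule.

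**3. How much testing.** PIF efforts at each of Visits 2 and 3: 4 techniques x at least 3 = at least 12. Spirometry sessions: 1 before dosing + 3 after Trelegy + 2 after Ventolin = 6. Inspiratory capacity: 1 + 1 + 1 = 3.

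**4. Who decides after dosing.** The design is open label, and PIF is measured at Visit 1 and used for stratification. The judgement that decides whether an event counts as an SAE is made with treatment and PIF known.

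**5. Size.** Inputs from the documents: 30 subjects; Visit 2 at 1-8 days after Visit 1; Visit 3 at 12-14 days after Visit 2. Assumption, not in the documents: 0.3 to 0.6 severe exacerbations per patient-year.

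- Scheduled time: 1 + 12 = 13 days to 8 + 14 = 22 days.
- Patient-years: 30 x 13/365 = 1.07 to 30 x 22/365 = 1.81.
- Expected admissions: 1.07 x 0.3 = 0.32 to 1.81 x 0.6 = 1.09.

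That is about 0.3 to 1.1 admissions for severe exacerbation in the whole study. It counts all such admissions, whether or not they would qualify under the SAE item. The scheduled time leaves out the undated follow-up contact and the one-week rescheduling that Safety Data Collection allows.

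**The case against.** The strongest reply is that the first item already does most of the work. It covers any cause, and an admission after washout or a cardiac event after Ventolin plainly puts a subject at clinical risk. All events then go into a single table, so such an event would appear there. This largely stands. What it leaves open is the label: the first item depends on investigator judgement and states no seriousness criterion, so an event entering by that route need not be marked as serious. The section lists no data fields for any event, so its silence does not prove that seriousness goes unrecorded; the plan simply does not require it.

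Second, the categories overlap. The replacement therapy is Trelegy itself, and the SAE item includes the device, so deterioration from poor delivery through the Ellipta could qualify. That is true, but only if the investigator attributes the event to the product rather than to the underlying disease. It does nothing for events before the first study dose.

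Third, this is an exploratory study of 30 patients with about two weeks of treatment. Its endpoints are bronchodilator response and PIF measurement, and no safety analysis is planned beyond the table. That stands, and it keeps the point minor.

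Fourth, the restriction may reflect a supplier's reporting requirement. The documents do not say so, and such a subset could be drawn from an all-cause listing in any case.

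**Conclusion.** The point holds as a limited one. The plan states a single SAE rule conditioned on attribution to Trelegy Ellipta, and nothing else widens it. Followed as written, it cannot guarantee a complete all-cause count of serious adverse events. This rests on the text and on the visit schedule's placing of the first study dose at Visit 2. It does not rest on the exacerbation rate, which serves only to show that the numbers are small. Severity: a minor, cheap improvement.

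A reader might infer more, and the documents do not support it:

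- *That serious events outside the SAE rule go uncollected, or could not be assessed by intervention.* The first item would collect many of them, and they would be listed.
- *That an SAE table would under-count unequally by PIF group.* No separate SAE table and no safety comparison by PIF group is planned. Open-label attribution makes unequal classification possible, but nothing shows that it would occur.
- *That only one of several sources of risk is covered.* This counts the SAE item alone; the first item spans all of them.
- *That about one serious event would be missed.* The 0.3 to 1.1 figure counts all expected admissions under an outside rate. The number that would go unlabelled as serious is smaller by an amount the documents do not allow one to estimate.

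**What to change.** Reword the SAE item to collect every serious adverse event from consent to the end of follow-up, regardless of attribution. Record seriousness for every collected event. Record the investigator's causality assessment as a data field, with the options Trelegy/Ellipta, Ventolin, or other study procedure or medication change. Causality should no longer be a condition for collection. List the events in the existing non-statistical table; showing PIF group there is optional.

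The cost is amended wording, a few fields on the event form and perhaps one extra SAE form in 30 patients. No visit, test, dose or planned analysis changes.
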